9.4.2.1. Adverse Events

An AE will be assigned to a study intervention if it occurred on or after the first dose of the study intervention and before the first dose of the next study intervention. An AE will be assigned to

the last study intervention of the treatment sequence if it occurred on or after the first dose of the last study intervention.

AEs will primarily be assessed through the analysis of AEs reported in the 48 hours following the administration of study intervention. A supportive analysis will include AEs reported within 30 days after the last dose of the study intervention (and before the first dose of the next intervention if any).

An AE will be considered a TEAE if the AE began or worsened (increased in severity or became serious) on or after the date (and time, if known) of the first dose of study intervention. However, an AE that occurs more than 30 days after the Period 1 study intervention and before the date of the Period 2 study intervention and an AE that occurs more than 30 days after the Period 2 study intervention will not be counted as a TEAE.

An AE will be considered a TESAE if it is a TEAE that additionally meets any SAE criterion.

The number and percentage of participants with TEAEs in each study intervention will be tabulated by system organ class and preferred term and by system organ class, preferred term, and severity.

The number and percentage of participants with treatment-related TEAEs in each study intervention will be tabulated by system organ class and preferred term.

If more than 1 AE is coded to the same preferred term for the same participant on the same study treatment, the participant will be counted only once for that preferred term using the most severe and most related occurrence for the summarizations by severity and by relationship to study intervention.

Summary tables will be provided for participants with TESAEs and participants with TEAEs leading to discontinuation. Listings of all AEs, SAEs, and AEs leading to discontinuation by participant will be presented.

The definitions of an AE and SAE can be found in Section 10.3 (Appendix 3).

9.4.2.2. Clinical Laboratory Assessments

Descriptive statistics for clinical laboratory values (in SI units) at baseline and changes from baseline at postdose assessment will be presented by study intervention for each clinical laboratory assessment.

The criteria for potentially clinically significant laboratory values will be detailed in the SAP. The number and percentage of participants who have potentially clinically significant postbaseline clinical laboratory values will be tabulated by study intervention. The assessment will be presented in the last study intervention the participant received. The percentages will be calculated relative to the number of participants who have available nonpotentially clinically significant baseline values and at least 1 postbaseline assessment. The numerator will be the total number of participants with at least 1 potentially clinically significant postbaseline value. A supportive listing of participants with potentially clinically significant postbaseline values will be provided for the safety population.

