This visit will occur 4 days (-2/+4 days) after double-blind study intervention is taken for the second qualifying prodrome event. It can occur as early as 2 days after taking double-blind study intervention (after the 48 hour assessment has been completed) and as late as 8 days after taking double-blind study intervention; however, participants should be encouraged to come in for this visit as soon as possible after completing their 48 hour assessments.

If none or 1 qualifying prodrome event has been treated during the double-blind treatment period and the 60-day time period has ended, the site will call the participant to schedule an ET Visit.

Randomized participants who exit the study early for any reason, whether or not they have taken study intervention, should also receive these evaluations. The following study procedures will be carried out at the Posttreatment/ET Visit (Visit 4):

- Register the participant's visit in the IWRS
- Collect vital sign measurements (sitting and standing systolic and diastolic BP, sitting and standing pulse rate, respiration rate, temperature, and weight)
- Review concomitant medication
- Review and assess AEs
- Assess C-SSRS on eTablet (the Since the Last Visit assessment of the C-SSRS will be completed)
- Perform ECG
- Perform physical examination
- Collect blood and urine samples for clinical laboratory tests (chemistry, hematology, and urinalysis)
- Perform urine pregnancy test (for WOCBP only)
- Collect eDiary and ensure all recorded data has been sent
- Review eDiary entries and ensure all questions and assessments were completed
- Collect side effects diary. Review the side effects listed on the diary and enter identified AEs in EDC.
- Collect study intervention blister package; review compliance against the information collected in the eDiary

For those participants participating in the optional PK substudy:

• Collect the DBS samples that the participant collected at home and ensure that the collection dates and times are recorded in the eDiary

Unscheduled Visits

Additional examinations, laboratory assessments, and pregnancy tests may be performed as necessary to ensure the safety and well-being of the participants during the study. Unscheduled visit eCRFs should be completed for each unscheduled visit.

Instructions for Participants

Section 5.3.1, Section 5.3.2, and Section 5.3.3 list dietary restrictions and activity instructions for participants enrolled in the study.

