8.2.4. Clinical Safety Laboratory Assessments

- See Section 10.2 for the list of clinical laboratory tests to be performed and the SoA (Section 1.3) for the timing and frequency. Hematology, chemistry, urinalysis, and urine pregnancy tests will be conducted at the Screening Visit (Visit 1), Randomization Visit (Visit 2), and Posttreatment/ET Visit (Visit 4). Coagulation, and the urine drug screen will be conducted at the Screening Visit (Visit 1) only.
- The investigator or subinvestigator will assess the clinical significance of any values outside the reference ranges provided by the laboratory, and participants with abnormalities judged to be clinically significant will be screen failed or withdrawn from the study.

- Positive results on the urine drug screen (unless explained by previously reported concomitant medication use, such as opioids prescribed for migraine pain) will be excluded from the study.
- A positive pregnancy test at Visit 1 or Visit 2 will exclude the participant from participation in the study. Participants who are confirmed to be pregnant during the study will be withdrawn.
- The investigator must review the laboratory report, document this review, and record any clinically relevant changes occurring during the study in the AE section of the eCRF. The laboratory reports must be filed with the source documents. Clinically significant abnormal laboratory findings are those that are not associated with the underlying disease, unless judged by the investigator to be more severe than expected for the participant's condition.
- All laboratory tests with values considered clinically significant during participation in the study or within 30 days after the last dose of study intervention should be repeated until the values return to normal or baseline or are no longer considered clinically significant by the investigator.
 - If such values do not return to normal/baseline within a period of time judged reasonable by the investigator, the etiology should be identified and the sponsor notified.
 - All protocol-required laboratory assessments, as defined in Section 10.2, must be conducted in accordance with the laboratory manual and the SoA (Section 1.3) or laboratory manual.

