9.4.2. Safety Analyses

The safety analysis will be performed using the safety population and will be fully defined in the SAP. The safety parameters will include AEs, clinical laboratory tests, ECGs, vital signs, and the C-SSRS. For each of the clinical laboratory tests, vital signs, and ECG parameters, the last nonmissing safety assessment before the first dose of double-blind study intervention will be used as the baseline for all analyses of that safety parameter.

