9.4.2.6. Potential Hy's Law

Potential Hy's Law criteria within a 24-hour window is defined by elevated ALT or AST laboratory value that is $\geq 3 \times ULN$ and an elevated total bilirubin laboratory value that is $\geq 2 \times ULN$ and, at the same time, an alkaline phosphatase laboratory value that is $< 2 \times ULN$, all based on blood draws collected within a 24-hour period.

Potential Hy's Law criteria without time window (evaluation of drug-induced serious hepatotoxicity) is defined by maximum of postbaseline elevation of ALT or AST laboratory

value that is $\geq 3 \times ULN$, along with maximum of postbaseline total bilirubin laboratory value that is $\geq 2 \times ULN$.

Participants who meet the potential Hy's Law criteria after taking study intervention and to the end of study participation will be summarized. If participants have unscheduled laboratory results after Visit 4 that meet potential Hy's Law criteria, the participants will be included in analysis. Supportive tabular displays will also be provided.

Participants who meet the potential Hy's Law criteria will be summarized by study treatment. The assessment will be present in the last study treatment the participant received.

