### **9.3 Analysis of Laboratory Data**

#### **9.3.1 Clinical Laboratory Parameters**

Descriptive statistics for clinical laboratory values (in SI units) at baseline and changes from baseline at each assessment time point will be presented by study intervention for

each clinical laboratory assessment. An assessment will be assigned to the most recently administered study intervention.

- Hematology: Hemoglobin; hematocrit; red blood cell count; red blood cell indices (mean corpuscular volume, mean corpuscular hemoglobin, mean corpuscular hemoglobin concentration); white blood cell count, including differential (neutrophils, lymphocytes, monocytes, eosinophils, and basophils); platelet count
- Chemistry: Sodium, potassium, chloride, bicarbonate, glucose, blood urea nitrogen, creatinine, total bilirubin, alkaline phosphatase, aspartate aminotransferase, alanine aminotransferase, lactate dehydrogenase, creatine kinase, total protein, albumin, calcium, phosphorus, uric acid, total cholesterol, HDL, LDL, total triglycerides, eGFR (calculated by the central lab)
- Urinalysis: Specific gravity, pH.

Shift tables from baseline to end of study for these clinical laboratory parameters will be presented by study intervention for the following categories: low, normal, and high, which are categorized by the laboratory vendor based on reference ranges.

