### **9.3.3 Hepatic Laboratory Abnormalities**

The number and percentage of participants meeting each of the criteria provided in Table C-2 for postbaseline hepatic laboratory abnormalities will be summarized by study intervention group. The percentages will be calculated relative to the number of participants with at least 1 available postbaseline assessment. The numerator will be the total number of participants having at least 1 postbaseline value that meets the specific category.

A listing of participants with hepatic laboratory abnormalities will be provided for the safety population.

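### Sequence B completers' only scheduled postdose laboratory and ECG values are tabulated under placebo after these participants have taken ubrogepant, so the placebo column is not a ubrogepant-free comparator

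*Protocol*

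**What the plan says.** **Timing of tests.** The Schedule of Activities (Protocol 1.3) and Protocol 8.2.4 place chemistry, hematology and urinalysis at Visits 1, 2 and 4/ET. ECGs follow the same three visits. The Visit 3 procedure list in Protocol Section 8 contains neither. Participants who leave early are also due the Visit 4/ET evaluations. If the 60 days end with no event or one event treated, "the site will call the participant to schedule an ET Visit".

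**Baseline.** Under Protocol 9.4.2, "the last nonmissing safety assessment before the first dose of double-blind study intervention will be used as the baseline", so a change from baseline in a completer spans both doses.

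**Attribution.** Protocol 9.4.2.2 (laboratory) and 9.4.2.4 (ECG) say: "The assessment will be presented in the last study intervention the participant received". Protocol 9.4.2.6 (Hy's law) says: "The assessment will be present in the last study treatment the participant received". It also brings in "unscheduled laboratory results after Visit 4". SAP 9.3.1 and 9.6.1 say: "An assessment will be assigned to the most recently administered study intervention". SAP 9.3.3 says that "postbaseline hepatic laboratory abnormalities will be summarized by study intervention group" and gives no attribution rule of its own.

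**Objective.** The safety objective in Protocol Section 3 is a comparison of ubrogepant with placebo.

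**The concern.** In a two-period crossover with one blood draw after both periods, that draw reflects both treatments. Labelling it by the last treatment sends every Sequence B completer to the placebo column after exposure to ubrogepant. A liver abnormality that began after ubrogepant and is still present at Visit 4, or is first seen there, would count against placebo. This happens in the summary that Protocol 9.4.2.6 describes as its evaluation of serious drug-induced liver toxicity. A reader of the by-treatment table would naturally take the placebo column as a rate without ubrogepant, and for most of its members it may not be.

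The washout does not settle the matter for liver tests. Protocol 9.4.1.2 justifies the 7 days by half-life, which concerns drug still in the body. It says nothing about an enzyme elevation that outlasts the drug or appears late. The Protocol itself allows for slower courses: one withdrawal criterion in 7.1 turns on elevation lasting beyond 2 weeks, and 9.4.2.1 counts treatment-emergent events for 30 days after a dose unless the next dose comes first.

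**Working it through.** The documents give no figure for this point, so there is none to reproduce. The check rests on the visit schedule and on assumed completion rates.

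**1. Who is in each column (scheduled postdose value, last-treatment rule)**

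| Participant | Column | Ubrogepant taken before the draw? |
|---|---|---|
| Sequence A, two doses | ubrogepant | yes |
| Sequence A, one dose, attends ET | placebo | no |
| Sequence B, two doses | placebo | yes |
| Sequence B, one dose, attends ET | ubrogepant | yes |

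**2. Time from ubrogepant to the draw.** The two treated events are separated by 7 days or more, and Visit 4 falls 2 to 8 days after the second dose (Protocol Section 8). Sequence B completers: at least 7 + 2 = 9 days. Sequence A completers: 2 to 8 days.

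**3. Exposed share of the placebo column.** Let d be the share of treated participants who treat one event only (equal in both sequences) and a the ET attendance among them.

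Share = (1 − d) / [(1 − d) + d·a]

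- a = 1: the share is 1 − d. For d = 5%, 20%, 50% it is 95%, 80%, 50%.
- a = 0.5: 0.95/0.975 = 97%; 0.80/0.90 = 89%; 0.50/0.75 = 67%.

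Neither document gives d. The 20% in SAP 2.4 is an assumed share with no qualifying event, and the 7% in Protocol 9.2 is the share without a determinable primary endpoint. Neither is a one-dose share, so d stays an assumption.

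**4. Counts, for illustration.** Assume 240 treated per sequence (516 × 0.93 = 479.9, halved; the 7% is only a proxy here) and a = 1.

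| d | Sequence B completers shown as placebo | Never exposed | Ever exposed | Ever exposed but shown as placebo |
|---|---|---|---|---|
| 5% | 228 | 12 | 468 | 228/468 = 49% |
| 20% | 192 | 48 | 432 | 192/432 = 44% |
| 50% | 120 | 120 | 360 | 120/360 = 33% |

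**5. Effect on the contrast.** Let e be a ubrogepant-caused excess in the abnormality rate at an early draw, and f the fraction of it present at the late Sequence B draw. With a = 1, the rule puts an excess of (1 − d)·f·e into the placebo column, and that amount comes off the difference between columns.

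| | d = 5% | d = 20% | d = 50% |
|---|---|---|---|
| f = 0 | 0 | 0 | 0 |
| f = 0.5 | 48% of e | 40% of e | 25% of e |
| f = 1 | 95% of e | 80% of e | 50% of e |

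The documents give neither e nor f. Late ET draws in Sequence B one-dose participants could also lower the ubrogepant column. That depends on when they attend and is not caused by the attribution rule, so it is left out.

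**6. Unscheduled tests between doses.** Take a Sequence B participant with an abnormal value after ubrogepant and before placebo, who later takes placebo. The SAP rule works per assessment and gives ubrogepant. The Protocol rule refers to the participant's last treatment and, read literally, gives placebo. The two documents disagree on this case, and the SAP rule is not stated to extend to 9.3.3.

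**The case against.** The strongest reply is that the root cause is the visit schedule. One draw after two treatments cannot be assigned cleanly to either, and assigning it to the most recent is disclosed and consistent with how adverse events are assigned. The tables are descriptive; no test on laboratory data is planned. Individual cases stay visible through listings of significant and hepatic abnormalities, a listing of adverse events in participants with significant laboratory values, AESI reporting, and the supportive displays promised for Hy's law. Sequence is fixed at randomization, so prior exposure can be traced case by case. Harm also requires a laboratory effect present 9 days or more after a single dose, and the documents show none.

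Much of this stands. No case is lost, no bias is demonstrated, and no reanalysis can recover a clean contrast. For ECG, with a washout well beyond 5 half-lives, only the label is at issue. A reader might infer that the plan conceals a liver signal; the documents do not support that, because the loss is zero at f = 0 and f is unknown. Nor can it be said that the tables will carry no note of prior exposure: SAP 1.0 puts table specifications in a separate document.

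What does not stand is that listings answer the point. They support case review but leave the columns of the comparative table as they are, and neither document plans a laboratory table by sequence or by prior ubrogepant.

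**Conclusion.** The point holds as a mislabelled comparison that should be corrected. As planned, every Sequence B completer's only scheduled postdose laboratory and ECG value sits under placebo, at least 9 days after ubrogepant. The scheduled placebo values free of ubrogepant come only from Sequence A one-dose participants who attend ET, a group selected after randomization. This follows from the text and needs no assumption.

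The size does need assumptions. With equal completion and full ET attendance, one-dose shares of 5% to 50% make the exposed part of the placebo column 95% to 50%. Lower attendance raises it. The loss of contrast due to the rule runs from nothing to 95% of any true excess over the ranges tried, so the effect on the trial's safety conclusions cannot be quantified. The stronger claim, that the hepatic comparison is biased by a known amount, is not supported.

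**What to change.** In SAP 9.3.1 to 9.3.3 and the Hy's law summary:

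- Keep the last-treatment table. Add a footnote that the placebo column includes participants with earlier ubrogepant and is not a clean ubrogepant-versus-placebo contrast. Use the same footnote in SAP 9.6.1.
- Add a supportive table of Visit 4/ET hepatic abnormalities and potential Hy's law cases by sequence and doses taken: placebo only, ubrogepant only, placebo then ubrogepant, ubrogepant then placebo.
- Add a count of these abnormalities among all ubrogepant-exposed participants with a postbaseline value.
- Show sequence and days since ubrogepant for each flagged case.
- Reconcile Protocol 9.4.2.2 and 9.4.2.6 with the per-assessment rule in SAP 9.3.1 for unscheduled tests between doses, and state that this rule governs SAP 9.3.3.

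The cost is SAP wording and a few tables from data already collected, with no new visits or tests. There are limits. Events unrelated to ubrogepant will enter the ever-exposed count. The never-exposed group is small: with the 12, 48 or 120 people in the working, zero events would leave a one-sided 95% upper bound, 1 − 0.05^(1/n), of 22%, 6% or 2.5%. Without tests between the doses, the change makes the tables say what they measure but cannot supply the missing contrast.

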9.4.2.3. Vital Signs

Descriptive statistics for vital signs (sitting and standing systolic and diastolic BP, sitting and standing pulse rate, respiration rate, temperature, weight, and body mass index) at baseline and changes from baseline at postdose assessment will be presented by study intervention.

Vital signs values will be considered to be potentially clinically significant if they meet both the observed-value criteria and the change-from-baseline-value criteria that will be detailed in the SAP. The number and percentage of participants who have potentially clinically significant postbaseline vital sign values will be tabulated by study intervention. The assessment will be presented in the last study intervention the participant received. The percentages will be calculated relative to the number of participants who have available nonpotentially clinically significant baseline values and at least 1 postbaseline assessment. The numerator will be the total number of participants with at least 1 potentially clinically significant postbaseline value. A supportive listing of participants with potentially clinically significant postbaseline values will be provided for the safety population.

9.4.2.4. Electrocardiograms

Descriptive statistics for ECG parameters (heart rate, PR interval, QRS interval, RR interval, QT interval, QTcB, and QTcF) at baseline and changes from baseline values at postdose assessment will be presented by study intervention.

The criteria for potentially clinically significant ECG values will be detailed in the SAP. The number and percentage of participants who have potentially clinically significant postbaseline ECG values will be tabulated by study intervention. The assessment will be presented in the last study intervention the participant received. The percentages will be calculated relative to the number of participants who have available nonpotentially clinically significant baseline values and at least 1 postbaseline assessment. The numerator will be the total number of participants with at least 1 potentially clinically significant postbaseline value. A supportive listing of participants with potentially clinically significant postbaseline values will be provided for the safety population.

9.4.2.5. Suicidality Assessment

For the C-SSRS, the number of participants with suicidal ideation and suicidal behavior in lifetime history and after taking double-blind study intervention will be summarized by study intervention for the safety population. The assessment will be presented in the last study intervention the participant received. A supportive listing of participants with suicidal ideation or suicidal behavior will be provided for the safety population.

9.4.2.6. Potential Hy's Law

Potential Hy's Law criteria within a 24-hour window is defined by elevated ALT or AST laboratory value that is $\geq 3 \times ULN$ and an elevated total bilirubin laboratory value that is $\geq 2 \times ULN$ and, at the same time, an alkaline phosphatase laboratory value that is $< 2 \times ULN$, all based on blood draws collected within a 24-hour period.

Potential Hy's Law criteria without time window (evaluation of drug-induced serious hepatotoxicity) is defined by maximum of postbaseline elevation of ALT or AST laboratory

value that is $\geq 3 \times ULN$, along with maximum of postbaseline total bilirubin laboratory value that is $\geq 2 \times ULN$.

Participants who meet the potential Hy's Law criteria after taking study intervention and to the end of study participation will be summarized. If participants have unscheduled laboratory results after Visit 4 that meet potential Hy's Law criteria, the participants will be included in analysis. Supportive tabular displays will also be provided.

Participants who meet the potential Hy's Law criteria will be summarized by study treatment. The assessment will be present in the last study treatment the participant received.

